### 7.2.2.1 Instructions for Specimen Storage

InPouch cultures will be stored in an incubator (37°C) at the clinical and laboratory sites until final result is recorded. Positive baseline specimens will be processed and stored frozen (-70 °C or colder) at each laboratory site until shipment to NYU. Gram stain slides are stored at room temperature at the laboratory sites until shipment to LSUHSC lab for reading. Gram stains will be read at LSUHSC. TV specimens for future microbiota studies (FMS) will be stored frozen (-70 °C or colder) at each laboratory site until annual shipment to LSUHSC where they will be stored frozen (-70 °C or colder) until future microbiota research resumes. Participants will have the ability to opt out of their FMS specimen storage/usage during the consent procedures. There will be a paragraph in the consent that outlines storage and use of frozen specimens, participants may choose to not have their specimens stored for long term use and still be able to participate in the study. If the participant opts out of future use of specimens, this will be indicated in REDCap and laboratories will be alerted to that status. At the end of the study, specimens of women who did not consent for specimen storage will be disposed of.

### 7.2.2.2 Specimen Shipment Preparation, Handling and Storage

InPouch Culture – InPouch cultures will be collected at the clinic sites and processed at the clinics' corresponding laboratories. Once collected, the culture will be placed in an incubator at the clinics with a regulated temperature of 37°C.

InPouch specimens are couriered to the corresponding laboratories where trained technicians will be required to obtain at least 3 readings separated by at least 24 hours within a 7 day period or until a positive TV pouch result. A diagnosis of TV will be made after the first positive pouch reading. If all InPouch readings within the 7 day period are negative, the woman will be considered TV negative. The pouches will be labeled with the study identification number and date of collection. Results from all reads will be kept in a laboratory log at each site.

Gram stain - Once the Gram stain slides are received at the LSUHSC they will be examined under low power magnification to find areas that have a concentrated amount of material to yield accurate readings. Then under oil immersion, 5 noncontiguous fields are examined that are representative of the material seen on the slide. These data are entered into the laboratory data form for each field. Results are entered into REDCap which calculates the Nugent score. Gram stain results will not be used for the clinical diagnosis of BV; they will only be used for research purposes.

T. vaginalis susceptibility testing - [name], of the CDC's parasitology laboratory, will

Version: 11.0

Version date: 1/2/17

perform susceptibility testing on the viable specimens of women who have a repeat infection at follow-up. Upon arrival at the CDC, parasites will be prepared according to CDC protocol. In brief, they will be cultured in modified Diamond's TYM medium at 37°C and transferred every 2 days until an axenic culture is obtained. Duplicate assays for drug resistance will be performed and isolates will be cryogenically preserved in Diamond's TYM medium supplemented with 5% dimethyl sulfoxide (DMSO) and agar. Metronidazole susceptibility will be assessed separately for each isolate in this study, after log growth is achieved. In brief, a stock solution (32 mg/ml) of metronidazole will be prepared in DMSO. Trichomonads ( $10^4$ ) will be added to two-fold serial dilutions (400-0.2 µg/ml) of metronidazole in 96-well plates. After incubation, the plates will be examined using an inverted microscope to determine the MLC, the lowest drug concentration at which no motile trichomonad was observed. Metronidazole susceptibility is defined by a MLC from 0.2 to 25 µg/ml. Low to moderate metronidazole resistance was defined by a MLC from 50 to 100 µg/ml. High metronidazole resistance was defined by a MLC 200 µg/ml or greater. The prevalence of in-vitro drug resistance will be compared by treatment study arm using chi-square test to determine if there is any indication drug resistance could account for some of the treatment failure. If the rates are similar by arm, we will ignore this potential confounder.

Prepping of InPouch specimens for TV genotyping- All positive InPouch cultures will be allowed to grow to a minimum of 50 parasites/field for up to 7 days. Then, 3 ml of the InPouch culture will be removed from the pouch and spun down. The pellet will then be resuspended in 2ml of 10% DMSO in fresh Diamond's media supplemented with 10% Horse serum. The suspension will then be split between two internally-laced cryotubes and stored at -70°C or colder until shipped. The stabilates will be sent to NYU on dry ice overnight and shipments will follow all standard regulations for shipment of Category B biological substances. Each clinical site laboratory will perform the specimen prep and batch freeze. Frozen specimens will be shipped to NYU according to a schedule determined by the PI.

TV Genotyping methods - Until recently, genotyping of *T. vaginalis* was limited by the crudeness of the genotyping techniques, e.g. RAPDs and RFLPs. These methods are highly sensitive to contaminating DNA or to slight variations in assay conditions, which influence their ability to accurately characterize *T. vaginalis* isolates. A recently developed panel of 21 *T. vaginalis*-specific microsatellites now provides a sensitive, reproducible, highly discerning set of genetic markers to accurately determine isolate-specific haplotypes and mixed genotype infections. Because of the high polymorphism of these markers and the number of loci that can be assayed, minor variations in haplotypes can be detected, allowing for high-resolution discrimination between related strains. [name] laboratory at NYU will genotype baseline and repeat infection specimens from all patients testing positive for TV at follow-up (~40 per year, ~120 total over 3 yrs). Frozen stabilates will be sent to NYU overnight and shipments will follow all standard regulations for shipment of Category B biological substances. Both isolates from each individual will be genotyped at 11 MS loci as described with minor modifications. Briefly, microsatellite-specific NAAT reactions will be performed for each locus using fluorescently labeled primers, and fragment length polymorphisms at the loci will be measured

Version: 11.0

Version date: 1/2/17

by capillary electrophoresis on an ABI 3130xl sequencer and scored using GeneMapper 4.0.

The haplotypes determined for the baseline and repeat infection will be compared to make inferences about the origin of reinfection. In addition, ~120 non-repeat infections (~40 each year) will also be genotyped to identify local population genetic characteristics and address the issue of confounding population structure.

NAAT swabs will be placed in a GenProbe vaginal collection tube and stored at 2-30°C. Swabs will be couriered daily from the clinic to the clinical laboratories and shipped at least monthly to the LSUHSC or UAB laboratory. Shipment will follow all Category B shipping restrictions. Upon arrival, DNA isolation will be performed using published methods and nucleic acid diagnostic results will be returned within one week.

Future microbiome study (FMS) swab – The vaginal swab will be placed in a tube containing 100ul of nucleic acid preservative. The tube will be maintained at room temperature following the manufacturer's recommendations until transport to the laboratory where it will be frozen at -70°C or colder until processing for the extraction of DNA

### **7.3 Substudies**

There are presently no sub-studies but the FMS may be added, pending provision of funding.

## **8 STUDY SCHEDULE**

### **8.1 Screening**

Per standard clinic protocol at each site, a patient's clinical examination will include testing for TV. Pregnancy testing by the clinic will follow their standard clinical care guidelines. If the patient self-reports that she is HIV negative, is not pregnant as determined by clinical protocol, not treated for BV and TV positive by wet prep, she will be referred by her clinician to the study personnel for potential enrollment. At sites where NAAT screening is performed, women may be referred because of a NAAT TV+ result. Study staff will discuss the study with the patient, review eligibility criteria and obtain informed consent.

### **8.2 Enrollment/Baseline**

The study will be described to potential participants by study staff and any questions will be answered and documented in the study records. Each site has an eligibility checklist for the study staff to use to confirm eligibility. As part of her eligibility checklist, staff will determine if a potential participant was given a pregnancy test at her clinical visit and confirm that the test was negative or that she had a hysterectomy or is post-menopausal for at least two years. If the woman is willing to participate and is eligible for the study, staff will obtain informed

Version: 11.0

Version date: 1/2/17

consent and provide a copy to participant. After consent is obtained, if a woman did not provide a urine pregnancy test as part of her clinical visit or meet the other criteria to determine she was not pregnant, she will be asked to provide a urine sample for testing. If the test is positive, women will be told that she is ineligible to continue with the study protocol since pregnancy is an ineligibility criterion. Study staff will provide her with her baseline compensation and refer her for pregnancy counseling as per each clinic's standard of care. The participant will be withdrawn prior to randomization and her randomization number will be used for the next participant. A participant may also be withdrawn from the study prior to randomization if she is found to meet other ineligibility criteria post-consent and pre-randomization. In these cases, she would receive her compensation and her randomization number would be used for the next participant.

If the participant is negative for pregnancy, she will undergo the audio computer assisted self-interview (ACASI). This survey will take approximately 30-45 minutes to complete and will be conducted after the clinical exam and written informed consent is obtained but before randomization to treatment. Information elicited will include detailed information about participants' demographics, socioeconomics, STI risk behavior and symptoms, substance use, and birth control methods, as well as partner specific information about sexual behavior, condom usage, and partnership status.

Women will be asked to self-collect vaginal swabs for Gram stain testing, In Pouch, TV NAAT and FMS. The participant will be given three or four sterile swabs and tubes and instructed on how to self-swab, place the swab in the tubes and return to the study office.

Study staff will process the specimens: for Gram stain, the swab will be carefully rolled by study staff over a predefined area of a glass slide, air dried, and stored in a slide cover; for FMS, the swab will be placed in a tube with preservative; for InPouch, the swab will be placed in the culture medium; for NAAT, the swab will be placed in the GenProbe tube. The specimens will be labeled with study identification numbers and dates of collection.

She will then be randomized to treatment arm (Single dose or 7 day dose). A blocked randomization scheme will be used to avoid "runs" in the randomization process. Pre-numbered, sealed envelopes will be selected sequentially and opened for each participant who will then be enrolled in the indicated arm.

If a woman is randomized into the single oral dose MTZ arm, she will be given the 2 g dose of MTZ and asked to ingest it under direct observation. If a woman is randomized into the 7 day oral dose MTZ arm, she will be given the 500 mg BID for 7 days and asked to ingest the first dose under direct observation.

All participants will receive the same counseling: to refrain from unprotected sexual intercourse until 1 week after they and their partner(s) complete the medication, to refrain from alcohol consumption while taking the medication and for 24 hours after completion; MTZ-related adverse events will be discussed including rash, dizziness, headache, diarrhea, nausea, vomiting, fatigue, upset stomach, dark red-brown urine, and change in taste sensation (metallic taste) or dry mouth. It will also be explained that MTZ can cause urine to darken in color but that this effect is not harmful. Participants in the 7-day arm will be given additional counseling on the importance of taking all doses of the medication.

If a participant's clinical TV positive test result is not confirmed TV-positive by InPouch culture or NAAT, she will be withdrawn from the study. These testing procedures and de-enrollment potential will be fully explained in the consent form. Women will receive \$20 compensation after completion of the baseline enrollment visit. Women will receive a study contact card that has all contact information for study personnel so that she may contact staff in case of appointment change, questions, or adverse events. She will be instructed to keep this card during the course of the study period. If she is withdrawn, she will keep her baseline compensation but told she will not need to attend her follow-up visits.

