*Protection against physical risk* - For the specimen collection, women will be instructed on proper collection techniques and will collect specimens in a private and clean room which will be maintained at a comfortable temperature. Women will be counseled about the investigational dose provided and potential side effects and adverse reactions will be described. Participants will be advised to contact their provider if any such events occur. At any time a woman wishes to discontinue participation in the study, she may with no consequences to her primary health care. For the danger of abuse from a sexual partner, women will be reminded that if they feel that any of their partners will have such a reaction, they should not tell them about her TV infection; she will also be referred to additional counseling as needed per clinic protocol.

Pregnancy and breastfeeding are exclusion criteria. Women of child bearing potential who have not been tested for pregnancy during her clinic visit on the day of enrollment will be tested for pregnancy by study staff (post-consent and pre-randomization) to ensure that she is not pregnant. Women who have had a hysterectomy or are post-menopausal for at least two years will not be required to take a pregnancy test. Staff will ask women about their breast feeding status prior to enrollment. Any woman who is breast feeding will not be eligible for the study. Women will be advised to use two forms of birth control while taking study medications.

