#### **6.4.2 Precautionary Medications and Procedures**

If the participant was not tested for pregnancy during her clinical visit and she is of child bearing potential, she will be tested by study staff after consent and pre-randomization to ensure that she is not pregnant. Women who have had a hysterectomy or are post-menopausal for at least two years will not have pregnancy testing. If it is determined that an enrolled participant is pregnant per her study pregnancy test, she will receive her baseline compensation and be administratively withdrawn from the study. These women will not receive a study ID number. Participants will be advised that alcohol should be avoided because metronidazole and alcohol together can cause severe nausea, vomiting, cramps, flushing, and headache. Metronidazole

Version: 11.0

Version date: 1/2/17

can increase the blood thinning effects of warfarin (Coumadin) and increase the risk of bleeding probably by reducing the breakdown of warfarin. Cimetidine (Tagamet) increases blood levels of metronidazole while cholestyramine reduces blood levels of metronidazole by reducing its absorption. Metronidazole blocks the breakdown of propylene glycol in the liver leading to accumulation of propylene glycol in blood. Accumulation of propylene glycol could cause seizures, increased heart rate, and lead to kidney failure. Metronidazole increases the blood levels of carbamazepine (Tegretol, Tegretol XR, Equetro, Carbatrol), lithium (Eskalith, Lithobid) and cyclosporine through unknown mechanisms. Serious reactions may occur if these drugs are taken with metronidazole

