# **7. STUDY PROCEDURES/EVALUATIONS**

## **7.1 Clinical Evaluations**

Baseline clinical evaluation will be provided during regularly scheduled clinical exam prior to enrollment including screening for TV.

At enrollment, women will be asked to provide self-collected vaginal swabs for InPouch culture, NAAT, Gram stain testing for bacterial vaginosis (BV) and storage for future microbiota studies (FMS). The same procedure will be done at 4 week and 8 week follow up visits, however, at 4 weeks the sites will have the option to obtain an additional vaginal swab for wet prep testing for TV.

At each visit, medical records will be abstracted (when those records are available) for clinical data which may include signs/symptoms and co-infections.

If a participant is positive by InPouch culture at her Test of Cure visit, and she has a viable organism, it will be tested for metronidazole sensitivity.

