## **13.2 Informed Consent Process**

After the clinic provider refers a potential participant to the study staff, the study staff will provide a description of the study and what participation involves and check eligibility criteria. If a woman is eligible and interested in enrolling, informed consent will be obtained. Study staff, who are trained in consent procedures and have participated in an institutional human subjects protection course will obtain consent. First, there will be a more detailed discussion of what the study involves. Next, staff will review the consent form including the procedures, risks, and benefits that may be anticipated. Staff will answer any questions that the woman may have and make certain she understands that she does not have to be in the study if she chooses not to be and non-participation will not affect her care at the clinic. Non-English speakers are excluded from participation in this study. If a woman has a low literacy level, there is a provision and signature line that the consent form has been fully read to the participant. The consent form will be signed and a copy will be given to the participant. The subjects should have the opportunity to discuss the study with their surrogates or think about it prior to agreeing to participate. The subjects may withdraw consent at any time throughout the course of the study. A copy of the informed consent document will be given to the subjects for their records.

A consent form template with suggested language for the clinical sites' consent forms will be approved by Tulane IRB. Site specific consent forms will be IRB approved at the study site by their specific the clinical institution's IRB (i.e. Louisiana State University Health Sciences Center, University of Mississippi Medical Center, the Mississippi State Department of Health and University of Alabama at Birmingham) and acknowledged by Tulane University IRB.

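### Section 2.3.1 accepts a clinic pregnancy test only if done on the enrollment day; 6.4.2 and 8.2 omit that condition, so later-day enrollees need not be re-tested under 8.2

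*Combined protocol and SAP*

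**What the plan says.** Four sentences in the combined protocol and SAP bear on whether a woman has a pregnancy test before randomization.

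- **2.3.1 Potential Risks**, under protection against physical risk: "Women of child bearing potential who have not been tested for pregnancy during her clinic visit on the day of enrollment will be tested". Study staff do this test after consent and before randomization.
- **6.4.2 Precautionary Medications and Procedures**: "If the participant was not tested for pregnancy during her clinical visit and she is of child bearing potential", study staff test her.
- **8.2 Enrollment/Baseline, eligibility checklist**: "staff will determine if a potential participant was given a pregnancy test at her clinical visit and confirm that the test was negative". Hysterectomy, or two or more years past menopause, is the alternative.
- **8.2 Enrollment/Baseline, after consent**: "if a woman did not provide a urine pregnancy test as part of her clinical visit or meet the other criteria", she is asked for a urine sample.

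On clinic testing, section 8.1 says: "Pregnancy testing by the clinic will follow their standard clinical care guidelines". On timing, section 7.1 says: "Baseline clinical evaluation will be provided during regularly scheduled clinical exam prior to enrollment including screening for TV". Section 8.1 gives same-visit wet prep as one referral route and adds another: "At sites where NAAT screening is performed, women may be referred because of a NAAT TV+ result". Section 13.2 says of consent: "The subjects should have the opportunity to discuss the study with their surrogates or think about it prior to agreeing to participate".

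**The concern.** The enrollment-day condition stands in the risk section but not in the sections that tell staff what to do. If a woman enrolls some days after her clinic visit, her earlier negative test satisfies 8.2 however old it is. She could have conceived, or an early pregnancy could have become detectable, in the interval.

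What is at stake is a safety eligibility rule. Pregnancy is an exclusion in 5.1.2, and section 9.1 lists pregnancy in a woman who tested negative at entry among three main safety concerns. Section 2.3.1 says that metronidazole has been used safely in the first trimester. It also says that pregnancy outcomes have not been systematically described and that the label contraindicates use in that period. The same section advises two forms of contraception during study medication; no section describes study advice for the time between the clinic visit and enrollment.

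There is also a compliance problem. Section 14.7 does not allow deviations and requires them to be reported. For a later-day enrollee, following 8.2 to the letter departs from 2.3.1.

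**Working it through.** No figure in the plan is in dispute, so the check is a comparison of texts.

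**Step 1: the four sentences side by side.**

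| Place | Clinic test that is accepted | Date condition |
|---|---|---|
| 2.3.1 | At a clinic visit on the enrollment day | Yes |
| 6.4.2 | At her clinical visit | No |
| 8.2, checklist | At her clinical visit, negative | No |
| 8.2, after consent | As part of her clinical visit | No |

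One of the four carries the condition and three do not. The checklist sentence is an eligibility check rather than a trigger for the study test. Counting triggers only, one of three carries it.

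**Step 2: apply the rules to cases, for a woman of childbearing potential.**

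| Case | Under 2.3.1 | Under 6.4.2 and 8.2 |
|---|---|---|
| Negative clinic test, enrolled that day | No study test | No study test |
| No clinic test | Study test | Study test |
| Negative test at an earlier visit, enrolled later, no new clinic test | Study test | No study test |
| Negative test at an earlier visit, returns through a new clinic visit with its own negative test, enrolled that day | No study test | No study test |

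The rules conflict only in the third case.

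**Step 3: can the third case occur?** No section says that it does. No section rules it out either.

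- Section 7.1 puts the clinical exam before enrollment but does not say on the same day. This is weak evidence, since it gives only the order.
- Section 13.2 lets a woman think before agreeing. This is also weak, since it is general consent language.
- Section 8.1 allows referral on a NAAT result, separately from wet prep. This is the substantive route. The turnaround of the clinics' screening NAAT is not stated.
- No section caps the interval between clinic visit and enrollment. By contrast, 5.1.2 does date-limit prior TV or BV medication, at 14 days.

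**Step 4: which visit is the clinical visit?** Inclusion criterion 5.1.1 uses the term for the visit at which the woman tested TV positive. For a NAAT referral, that points to the visit when the screening sample was taken, not to a return visit.

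**Step 5: size.** The documents give neither the share of women enrolled on a later day nor the interval, so the number affected cannot be estimated. The burden of the fix can be bounded. At most one extra test per enrolled woman gives 1664 × 1 = 1664. If every clinic test is already done on the enrollment day, the number is 0.

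**The case against.** The strongest reply is that a protocol is read as a whole. Section 2.3.1 binds sites as much as 8.2 does and can be taken to identify the clinical visit as the one on the enrollment day. No sentence expressly accepts an older test. The plan mostly describes one continuous flow: women found positive at a routine exam are referred by their clinician to study staff in the same clinic, usually on a wet prep. The conflict needs three things together: enrollment on a later day, a negative test at the earlier visit, and no new test on return. Other protections exist. Section 8.1 requires that the woman is not pregnant by clinic protocol, and 8.6 provides for follow-up of mother and child. A same-day test also misses very early conception. The site checklists and the Manual of Procedures are not among the documents and may already carry the date.

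Much of this stands. The safeguard is in the protocol, the frequency is unknown, and the gap in practice may be small or nil. What does not stand is the claim that the sections already agree. Nothing in the text says that 2.3.1 defines the visit for every other section, and 5.1.1 points the other way for NAAT referrals. The remaining risk after a same-day test is no reason to add the avoidable risk of an older one. If same-day enrollment was always intended, stating it costs nothing.

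**Conclusion.** The concern holds and should be fixed. It is an inconsistency in a safety eligibility rule: the date condition is in one of four sentences and missing from the three that staff would follow at enrollment. For a woman with a negative test at an earlier clinic visit and no new test, 2.3.1 requires a study test and 8.2 does not.

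The textual difference is certain. That it affects anyone rests on the assumption that some women enroll on a later day than their clinic visit, which the plan allows but does not state. No number of affected women can be given. The endpoint, randomization and analysis do not depend on it.

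**What to change.** Add the words *on the day of enrollment* after the reference to the clinical visit in three places: the testing sentence in 6.4.2, the checklist sentence in 8.2 and the post-consent sentence in 8.2. A woman of childbearing potential whose clinic test was on an earlier day then has the existing study urine test after consent and before randomization. Make sure the eligibility checklist records the date of the pregnancy test, if it does not already.

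The cost is one phrase in three sentences, a check of the checklist, and some extra urine tests. The test is already a study procedure. Women tested by the clinic on the enrollment day, women the study already tests, and women exempt by hysterectomy or menopause need no additional test.

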### **9.4.1 Methods and Timing for Assessment**

Adverse events reported by participants will be recorded and reported to the institutional IRBs according to their reporting requirements. At each follow up visit, staff will inquire if any metronidazole was taken since last visit and if there were any adverse events from taking the medication. This information will be recorded in study data.

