## **9.10 Stopping Rules for an Individual Participant/Cohort**

Criteria for Discontinuation of Study Agent(s)/Intervention(s):

-if they are randomized to an arm and are unable to tolerate the dose the study agent will be discontinued.

Criteria for Withdrawal of a Participant:

-if they become incarcerated and are unable to attend follow up visits

-if any clinical adverse event, laboratory abnormality, concurrent illness, other medical condition or situation occurs such that continued participation in the study would not be in the best interest of the participant.

-if a woman is found to be pregnant after consent but prior to randomization

-if a woman is found to be ineligible after consent but prior to randomization

-if a participant initial TV positive wet prep result is not confirmed by either InPouch culture or TV NAAT test from her enrollment visit

Version: 11.0

Version date: 1/2/17

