# **10. Clinical Monitoring Structure**

## **10.1 Site Monitoring Plan**

The Principal Investigator and Tulane study staff under the direction and supervision of the PI, will conduct regular site monitoring to ensure human subject protection and that study procedures are being conducted as per protocol and Manual of Procedures as outlined in section 12.0. For the first 4 months of enrollment, weekly conference calls will be held with investigators and study personnel at sites to ensure start up activities are following protocol, any questions can be answered, and clinic flow and specific clinical issues can be addressed. The PI and Program Manager are available at any time via email or cell phone to address any urgent issues. Quarterly site visits will be conducted by the PI, or her designee. At these visits, at least 10% of study charts will be pulled and reviewed, all consent forms will be reviewed and consent procedures will be discussed. There will also be a systematic review of enrollment statistics (i.e., number of eligible patients, refusal log, ineligibility log). Weekly data transfer to the research office at Tulane University will allow the program manager to review data collected for any errors or discrepancies and report back to sites to resolve any inconsistencies.

Women will be systematically asked if they experienced any of the common side effects on the TOC CRF.

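### Women dosed at baseline and later withdrawn as TV-unconfirmed are released from the visits at which adverse events are solicited, so solicited safety data are incomplete in both arms

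*Combined protocol and SAP*

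**What the plan says.** **Dosing.** Section 8.2 (Enrollment/Baseline) places randomization and treatment at the baseline visit. In the single-dose arm "she will be given the 2 g dose of MTZ and asked to ingest it under direct observation". In the 7-day arm "she will be given the 500 mg BID for 7 days and asked to ingest the first dose under direct observation", and the other doses are taken at home.

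**Confirmation and withdrawal.** The confirming swabs are collected at the same visit, before randomization, but are read later. Section 8.2 says that a woman whose clinical positive "is not confirmed TV-positive by InPouch culture or NAAT, she will be withdrawn from the study". Section 9.10 repeats the rule among the withdrawal criteria: "if a participant initial TV positive wet prep result is not confirmed by either InPouch culture or TV NAAT test from her enrollment visit". The consequence for follow-up is in section 8.2: "If she is withdrawn, she will keep her baseline compensation but told she will not need to attend her follow-up visits".

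**Adverse-event collection.** Section 9.4.1 says: "At each follow up visit, staff will inquire if any metronidazole was taken since last visit", and whether it caused adverse events. Section 10.1 says: "Women will be systematically asked if they experienced any of the common side effects on the TOC CRF". These are the only places where active questioning is described.

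**The concern.** Leaving an unconfirmed woman out of the efficacy analysis can be defended, because the deciding swabs were taken before she was allocated. That reasoning does not extend to safety: she has taken the study drug, and what happened afterwards is relevant whatever the laboratory later finds.

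The 7-day regimen is described as not FDA approved for TV (section 9.1) and as possibly carrying increased side effects (section 2.3.1). The trial runs under an IND. The halting rule in section 9.9 depends on judging whether side effects exceed the normal level, and that judgment is best made on counts from everyone exposed. As written, the plan stops asking part of the exposed group for a reason unrelated to tolerability.

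**Working it through.** **1. Timing: does dosing precede confirmation?**
- Dosing: the day of the baseline visit (8.2).
- InPouch: negative only after all readings within a 7-day period are negative (7.2.2.2).
- NAAT: shipped at least monthly, with results within one week of arrival (7.2.2.2).
- Withdrawal needs both tests to fail to confirm, so the slower one sets the date. That is about 1 week at the earliest and about 4 + 1 = 5 weeks at the latest.

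By then the single dose is complete and the 7-day course is mostly or wholly over.

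**2. Could she already have been asked?**
The TOC window opens 3 weeks after baseline (single dose) or 4 weeks (7-day dose) (8.3). Against a latest result at about 5 weeks, some women can complete TOC and answer the questions before they are found unconfirmed. The plan does not say whether their answers are kept.

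**3. Does another section close the gap?**
- 8.5 (Early Termination Visit) covers only women who refuse the intervention.
- 9.11 keeps data already collected, but is written for voluntary withdrawal and cannot supply answers never sought.
- 11.13 states intent-to-treat and defines no safety population.
- The contact card (8.2), advice to contact the provider (2.3.1) and recording of participant-reported events (9.4.1) all depend on the woman coming forward.

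None of these solicits events from the withdrawn woman.

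**4. The plan's number of women.**
Section 11.7 uses 16.2% versus 10.7% at 80% power. With two-sided alpha 0.05 and pooled variance, p̄ = 0.1345 and

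n = [1.960 × √(2 × 0.1345 × 0.8655) + 0.842 × √(0.162 × 0.838 + 0.107 × 0.893)]² / 0.055² = 603 per arm, or 1206 in total.

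1206 × 1.15 × 1.20 = 1664.3, matching the stated 1664. With 20% lost, 1664 × 0.8 = 1331 remain (the plan says 1332). The point does not depend on this calculation; it only supplies the base for the sizing below.

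**5. Size of the gap.**
The unconfirmed share u is not in the documents; 2% to 10% is an assumption. All 1664 are taken as dosed, and the 20% follow-up loss is taken to apply equally to unconfirmed women.

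| | u = 2% | u = 10% |
|---|---|---|
| Dosed, unconfirmed: 1664 × u | 33 | 166 |
| Per arm | 17 | 83 |
| Beyond planned loss: 1664 × u × 0.8 | 27 | 133 |
| Actively questioned: 1664 × (1 − u) × 0.8 | 1305 | 1198 |
| Nausea cases at 12%, all unconfirmed | 4 | 20 |
| Nausea cases at 12%, beyond planned loss | 3 | 16 |

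The 12% is the nausea figure in section 9.4 and serves as illustration only. These rows ignore women who reach TOC before the NAAT result, so they are upper figures for a given u.

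**6. Effect on precision.**
If an event is never seen in an arm, the approximate 95% upper bound on its rate is 3/n. With no unconfirmed women, 3/(832 × 0.8) = 0.45%. At u = 2% it is 3/(832 × 0.98 × 0.8) = 0.46%, and at u = 10% it is 3/(832 × 0.90 × 0.8) = 0.50%.

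**The case against.** The strongest reply is that this is a narrow completeness issue. Safety is not a stated objective or endpoint, the drug has over 40 years of use for TV, and serious events have their own expedited route once a site is aware of them (9.5.1). Confirmation rests on pre-randomization swabs, so the number of unconfirmed women should be similar in the two arms and the comparison is not systematically distorted. That stands, and it limits the point to completeness and precision.

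A reader might also infer several stronger things that the documents do not support:

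- **That these women leave safety ascertainment altogether, or are never asked.** Unprompted reporting remains, some may reach TOC first, and the wording releases a woman from visits without barring her.
- **That exposed pregnancies are lost.** No pregnancy test is listed among the follow-up procedures (7.1, 8.3), so no scheduled test is lost. Section 8.6 provides for following a woman found to have been pregnant at treatment and does not make this conditional on staying enrolled.
- **That they had no TV to treat.** Each had a positive clinic test (8.1), and section 2.3.1 acknowledges false negatives. Non-confirmation is not proof of absence.
- **That DSMB reports would understate exposure or events.** Nothing says withdrawn women are removed from those reports; the plan is silent.

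Not every case behind the 12% nausea figure would be a protocol adverse event either, because section 9.2 lists persistent nausea or vomiting.

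**Conclusion.** The gap is real but modest. Women are dosed before confirmation, and those later found unconfirmed are released from the only contacts at which adverse events are described as actively sought. Except for those who complete TOC before the NAAT result, they contribute only spontaneous reports. This holds in both arms and for any unconfirmed share above zero.

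The size rests on an assumed share. At 2% to 10% it is 33 to 166 dosed women, about 27 to 133 of them beyond the planned follow-up loss, and the loss of precision is small. The number unconfirmed should be about equal by arm; the number questioned before withdrawal could differ slightly because the TOC window opens a week earlier in the single-dose arm. The documents support incomplete solicited safety data, not a biased treatment comparison. Because the remedy is cheap, the change should be made.

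**What to change.** Amend sections 8.2 and 9.10 so that:

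1. Non-confirmation by both baseline tests excludes a woman from the efficacy analysis only.
2. She is released from swabs and clinic visits, but staff put the existing TOC side-effect and adverse-event questions to her by phone, for example at the withdrawal contact or within the TOC window. The TOC window is preferable, since recall is then closer to that of the other women.
3. Any safety data already collected, including from a TOC visit completed before the NAAT result, are kept.

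Add to section 11.13 a safety population of all randomized women who took at least one dose, reported by arm, with the number unconfirmed and the number of those reached by phone.

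**Cost.** A short amendment, a matching line in the consent form (which already explains possible de-enrollment), and one brief call per unconfirmed woman. Section 5.2 already provides for detailed contact information at baseline, and she has to be contacted about withdrawal anyway. No extra swabs, visits or staff are needed, and no treatment rule changes. The downside is a little staff time, and phone rather than visit data for this group.
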